## SUMMARY OF CHANGES

### PRIMARY REASON(S) FOR THIS AMENDMENT:

Section Number (s)	Section Title(s)	Description of Change (s)	Rationale
1.0	TRIAL SUMMARY	After marketing approval of MK-3475, "clinical trial" will be replaced with "post-marketing clinical trial" and this study will be continued.	1) This amendment makes continuing patients use MK-3475 on this protocol between the approval and the availability of marketed product of MK-3475
2.1	Trial Design	Between the marketing approval of MK-3475 and 1) the delivery of marketed product of MK-3475 in each site, or 2) 6 months from marketing approval, whichever occurs first, the subjects can receive treatment of MK-3475 as post-marketing clinical trial drug.	2) Due to the requirement of Japanese regulation, after marketing approval of MK-3475, "clinical trial" will be replaced with "post-marketing clinical trial". 3) Patients can use study drug MK-3475 until the availability of marketed product of MK-3475 or 6 months from marketing approval, whichever occurs first.
5.8	Subject Withdrawal/Discontinuation Criteria	"The delivery of marketed product of MK-3475 in each site" and "6 months from marketing approval" is added to the criteria of discontinuation from the treatment of MK-3475.	
9.1	Investigational Product	After the time of the marketing approval of MK-3475, "clinical trial drug" of MK-3475 will be replaced with "post-marketing clinical trial drug". Until the delivery of marketed product of MK-3475 in each site, the subjects can receive treatment of MK-3475 as post-marketing clinical trial drug	

1.0	TRIAL SUMMARY	“1) the marketing approval of MK-3475, 2) the completion of safety follow-up or 3) the time when a possibility of entry to second course is lost, whichever occurs last” is added into the criteria of discontinuation of this study.	Study end is 1) the marketing approval of MK-3475, 2) the completion of safety follow-up or 3) the time when a possibility of entry to second course is lost, whichever occurs last.  More data becomes to be not required.
2.1	Trial Design		
5.8	Subject Withdrawal/Discontinuation Criteria		
1.0	TRIAL SUMMARY	The treatment of marketed product of MK-3475 is included to non-study cancer treatment  Good Post-marketing Study Practice (GPSP) is added and this study is to be conducted in conformance with GPSP	If patients start marketed product of MK-3475, safety follow-up for 30 days from the last dose of study drug MK-3475 should be required.  In Japan, by law, filling of re-examination is required, based on information after approval.  Post-marketing clinical trial is specified in GPSP and post-marketing clinical trial must obey GPSP.
2.1	Trial Design		
10.3	Compliance with Law, Audit and Debarment		
10.5	Quality Management System		
13.2	Investigator		

**ADDITIONAL CHANGE(S) FOR THIS AMENDMENT:**

Section Number-(s)	Section Title-(s)	Description of Change-(s)	Rationale
5.2.1.2	Dose Modification (Escalation/Titration/Other)	Table 3 Dose Modification Guideline is updated. Instruction for Dose Modification is modified	Clarification and consistency in alignment with program level MK-3475 ECI guidance
5.6.1	Supportive Care Guidelines	Table 5 Recommended Approach to Handling Pneumonitis and Table 6 General Approach to Handling irAEs are deleted. Instruction for Supportive Care Guidelines is modified	
7.2	Assessing and Recording Adverse Events	Revised wording to provide further clarification on adverse event collection.	Clarification and consistency in alignment with program level MK-3475
4.2.1	Rationale for the Trial and Selected Subject Population	timing (at the start of this study) is added when newly therapies such as ipilimumab have not been approved yet in Japan	Therapies such as ipilimumab have been approved already in Japan now.

## 1.0 TRIAL SUMMARY

Abbreviated Title	Phase Ib Study of MK-3475 in Subjects with Advanced Melanoma
Trial Phase	Ib
Clinical Indication	The treatment of subjects with locally advanced or metastatic melanoma
Trial Type	Interventional
Type of control	No treatment control
Route of administration	Intravenous
Trial Blinding	Unblinded Open-label
Treatment Groups	MK-3475 2 mg/kg every 3 weeks (Q3W)
Number of trial subjects	Approximately 35 subjects will be enrolled.
Estimated duration of trial	The sponsor estimates that the trial will require approximately 10 months from the time the first subject signs the informed consent until the last subject's last visit.
Duration of Participation	Each subject will participate in the trial from the time the subject signs the Informed Consent Form (ICF) through the final protocol-specified contact. After a screening phase up to 4 weeks, eligible subjects will receive treatment on Day 1 of each 3-week dosing cycle. Treatment with MK-3475 will continue until the subject meets the discontinuation criteria such as 24 months of therapy completion, documented disease progression (per modified RECIST 1.1), or unacceptable toxicity, etc. Subjects who meet criteria for temporary discontinuation of study therapy after complete response (CR) may consider stopping trial treatment. These subjects may be eligible for re-treatment after experiencing disease progression at the discretion of the investigator if they meet the criteria for re-treatment for up to one year; this will be designated the Second Course Phase. After the end of treatment, each subject will be followed for a minimum of 30 days for adverse event monitoring (serious adverse events will be collected for up to 90 days after the end of treatment). Subjects who discontinue for reasons other than disease progression will have post-treatment follow-up for disease status until initiating a non-study cancer treatment (including the treatment of marketed product of MK-3475), disease progression, withdrawing consent, death, or the end of the study. All subjects will be followed by telephone for overall survival until death, withdrawal of consent, or the end of the study.

After marketing approval of MK-3475 for melanoma, “clinical trial” will be replaced with “post-marketing clinical trial” and this study will be continued. Between the marketing approval of MK-3475 for melanoma and 1) the delivery of marketed product of MK-3475 in each site, or 2) 6 months from marketing approval for melanoma, whichever occurs first, the subjects can receive treatment of MK-3475 as post-marketing clinical trial drug.

The end of the study of each subject is 1) the marketing approval of MK-3475 for melanoma, 2) the completion of safety follow-up or 3) the time when a possibility of entry to second course is lost, whichever occurs last.

## **2.0 TRIAL DESIGN**

### **2.1 Trial Design**

This is an open-label, non-randomized, multi-center Phase Ib study of MK-3475 in subjects with advanced melanoma to be conducted in conformance with Good Clinical Practices (GCP) and Good Post-marketing Study Practice (GPSP). Approximately 35 subjects will be enrolled in this trial to examine the safety and efficacy of the 2 mg/kg dose of MK-3475 administered every 3 weeks. The primary objectives of the trial are to determine the safety, tolerability, and overall response rate (ORR) per Response Evaluation Criteria in Solid Tumors version 1.1 (RECIST 1.1) in subjects with advanced cutaneous melanoma. The secondary objectives include the duration of response (DOR), progression-free survival (PFS) per RECIST 1.1, and the ORR, DOR, and PFS per immune-related response criteria (irRC), and overall survival (OS) in subjects with advanced cutaneous melanoma. As the exploratory objectives, the efficacy (ORR, DOR, and PFS) per RECIST 1.1 and irRC and OS in subjects with advanced mucosal melanoma, the pharmacokinetic (PK) properties of MK-3475, the presence of anti-MK-3475 antibodies, pulmonary radiographic changes and its features, and the relationship between candidate biomarkers (including PD-L1 expression) and anti-tumor activity of MK-3475 will also be evaluated. Subjects will be evaluated every 6 weeks starting at 12 weeks through 48 weeks, and after 48 weeks, every 12 weeks with radiographic imaging to assess response to treatment. Tumor response will be assessed using RECIST 1.1 and irRC by the central independent radiology review. RECIST 1.1 will be used by the local site to determine eligibility and modified RECIST 1.1 will be used to make treatment decisions (refer to Section 4.2.3.2). Adverse events will be monitored throughout the trial and graded in severity according to the guidelines outlined in the NCI Common Terminology Criteria for Adverse Events (CTCAE) version 4.0.

Treatment with MK-3475 will continue unless the subject meets the discontinuation criteria such as disease progression (evaluated by modified RECIST 1.1), unacceptable toxicity, or completion of 24 months of treatment with MK-3475 (refer to Section 5.8 for further details). Subjects who attain an investigator-determined confirmed CR may consider stopping trial treatment after receiving at least 24 weeks of treatment (Treatment Phase). Subjects who discontinue after at least 24 months of therapy for reasons other than disease progression or intolerance or who discontinue after attaining a CR may be eligible for up to one year of retreatment (Second Course Phase) after they have experienced radiographic disease progression. The decision to retreat will be at the discretion of the investigator only if no cancer treatment (including the treatment of marketed product of MK-3475) was administered since the last dose of MK-3475, the subject still meets the safety parameters listed in the Inclusion/Exclusion criteria and the trial remains open (refer to Section 7.1.5.2.1 for further details). After the end of treatment in Treatment Phase and Second Course phase, each subject will be followed for 30 days for adverse event monitoring (serious adverse events will be collected for 90 days after the end of treatment). Subjects who discontinue treatment for reasons other than disease progression will have post-treatment follow-up for disease status until initiating a non-study cancer treatment, disease progression, withdrawing consent, death, or the end of the study, whichever occurs first. Response and progression in the Second Course Phase will not count towards the ORR and PFS of the efficacy endpoint in

this trial. All subjects will be followed by telephone contact for overall survival until death, withdrawal of consent or the end of the study, whichever comes first. Clinical data may temporarily be locked to assess the efficacy endpoint, ORR per RECIST 1.1 for advanced melanoma when once all of the enrolled subject has either progression disease or has had an imaging 24 weeks after treatment initiation, whichever occurs first.

Participation in this trial will require submitting an archival tissue sample or newly obtained biopsy of a tumor lesion not previously irradiated for PD-L1 expression evaluation. This specimen will be evaluated at a central laboratory for expression status of PD-L1 by immunohistochemistry (IHC). Both PD-L1 positive and negative subjects will be enrolled in this trial, and the clinical activity in both subsets will be evaluated as a pre-defined subgroup analysis.

After marketing approval of MK-3475 for melanoma, “clinical trial” will be replaced with “post-marketing clinical trial” and this study will be continued. Between the marketing approval of MK-3475 for melanoma and 1) the delivery of marketed product of MK-3475 in each site, or 2) 6 months from marketing approval for melanoma, whichever occurs first, the subjects can receive treatment of MK-3475 as post-marketing clinical trial drug.

The end of the study of each subject is 1) the marketing approval of MK-3475 for melanoma, 2) the completion of safety follow-up or 3) the time when a possibility of entry to second course is lost, whichever occurs last.

Specific procedures to be performed during the trial, as well as their prescribed times and associated visit windows, are outlined in the Trial Flow Chart - Section 6.0. Details of each procedure are provided in Section 7.0 – Trial Procedures.

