## **5.8 Subject Withdrawal/Discontinuation Criteria**

Subjects may withdraw consent at any time for any reason or be dropped from the trial at the discretion of the investigator should any untoward effect occur. In addition, a subject may be withdrawn by the investigator or the Sponsor if enrollment into the trial is inappropriate, the trial plan is violated, or for administrative and/or other safety reasons. Specific details regarding discontinuation or withdrawal procedures; including specific details regarding withdrawal from Future Biomedical Research, are provided in Section 7.1.4 – Other Procedures.

A subject must be discontinued from the trial for any of the following reasons:

- The subject or legal representative (such as a parent or legal guardian) withdraws consent.
- The marketing approval of MK-3475 for melanoma, the completion of all safety follow-up or the time when a possibility of entry to second course is lost (e.g. the time of decision by investigator or subject for no enter to second course, the start of a new anti-cancer therapy, the delivery of marketed product of MK-3475 in each site, 6 months from marketing approval), whichever occurs last

A subject must be discontinued from treatment (but may continue to be monitored in the post-treatment follow-up portion of the trial) for any of the following reasons:

- Radiographic disease progression

Note: A subject may be granted an exception to continue on treatment with confirmed radiographic progression if clinically stable or clinically improved, please see Section 7.1.3.4

- Unacceptable adverse experiences as described in Section 5.2.1.2
- Intercurrent illness that prevents further administration of treatment
- Completed 24 months of treatment with MK-3475

Note: 24 months of study medication is calculated from the date of first dose. Subjects who stop MK-3475 after 24 months may be eligible for up to 1 year of additional study treatment if they progress after stopping study treatment provided they meet the requirements detailed in Section 7.1.5.2.1.

- Investigator's decision to withdraw the subject
- The subject has a confirmed positive serum pregnancy test
- Noncompliance with trial treatment or procedure requirements

- The subject is lost to follow-up
- Administrative reasons
- The delivery of marketed product of MK-3475 in each site
- 6 months from marketing approval for melanoma

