#### **7.1.5.4.3 Survival Follow-up**

Once a subject experiences confirmed disease progression or starts a new anti-neoplastic therapy, the subject moves into the survival follow-up phase and should be contacted by telephone every 12 weeks to assess for survival status until death, withdrawal of consent, or the end of the study, whichever occurs first.

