#### **8.1.1 Efficacy Analyses**

The full analysis set (FAS) population (defined as all subjects with a baseline scan with measurable disease and who either have a post baseline scan or discontinue the trial due to progressive disease or a drug-related AE) will serve as the primary population for the analyses of efficacy data in this trial. Overall response rate based on RECIST 1.1 will be used as the primary endpoint for efficacy assessment. A 95% confidence interval along with a one-sided p-value for testing the null hypothesis (ORR=10%) based on the binomial distribution will be provided for the response rate. The study is considered to have reached the efficacy objective if the corresponding p-value for testing the respective null hypothesis is less than 2.5%. An outline of the efficacy analysis strategy is presented in [Table 8](#) below.

Table 8 Primary Analysis Strategy for Efficacy Endpoints

Endpoint/Variable (Description, Time Point)	Statistical Method	Analysis Population	Missing Data Approach
Primary:			
Overall RECIST 1.1 response rate based on central radiology review	Exact test of binomial parameter	FAS	Subjects with missing data are considered non-responders
Secondary:			
Overall RECIST 1.1 response rate based on site assessment	Exact methods for binomial parameter	FAS	Subjects with missing data are considered non-responders
Progression-free survival (RECIST 1.1)	Summary statistics using Kaplan-Meier method	FAS	Censored at last assessment
Response duration (RECIST 1.1)	Summary statistics using Kaplan-Meier method	All responders	Non-responders are excluded in analysis
Overall survival	Summary statistics using Kaplan-Meier method	FAS	Censored at last assessment
Overall irRC response rate based on central radiology review	Exact methods for binomial parameter	FAS	Subjects with missing data are considered non-responders
Progression-free survival (irRC)	Summary statistics using Kaplan-Meier method	FAS	Censored at last assessment
Response duration (irRC)	Summary statistics using Kaplan-Meier method	All responders	Non-responders are excluded in analysis

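### Survival follow-up ends at marketing approval for most subjects already off treatment but continues for those on drug or eligible for Second Course, so the late Kaplan-Meier OS curve is biased upward; a minor point with a simple fix

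*Combined protocol and SAP*

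**What the plan says.** Section 2.1 defines a separate end of study for each subject, as the latest of three dates: marketing approval, the end of safety follow-up, and "the time when a possibility of entry to second course is lost, whichever occurs last". Section 5.8 repeats the rule and makes it mandatory, under the lead-in "A subject must be discontinued from the trial for any of the following reasons". Its examples of losing the Second Course possibility include "the start of a new anti-cancer therapy, the delivery of marketed product of MK-3475 in each site, 6 months from marketing approval".

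OS follow-up is tied to that date. Section 2.1: "All subjects will be followed by telephone contact for overall survival until death, withdrawal of consent or the end of the study, whichever comes first". Section 7.1.5.4.3 says the same of subjects who have progressed or started a new therapy: "contacted by telephone every 12 weeks to assess for survival status until death, withdrawal of consent, or the end of the study, whichever occurs first".

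Section 7.1.5.2.1 limits Second Course to two groups: subjects who stopped after a confirmed CR, and subjects with SD or better who stopped after 24 months for reasons other than progression or intolerance. Section 2.1 allows trial drug after approval until marketed product reaches the site or 6 months have passed, whichever is first. Section 7.1.5.4.1 then adds a safety visit about 30 days after the last dose.

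For OS, Tables 8 and 9 give Kaplan-Meier summaries in the FAS with the missing-data entry "Censored at last assessment". Section 8.2.9 says follow-up continues after the main analysis for duration of response and OS. No OS cut-off date is given.

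**The concern.** Kaplan-Meier estimation assumes that a subject censored at a given time has the same future risk of death as those who remain under observation. Here the length of survival follow-up depends on whether the subject is still on drug, or still eligible for Second Course, around the approval date. That status is strongly related to progression, and progression predicts death. Subjects with the worse outlook tend to leave the risk set at approval and those with the better outlook tend to stay, so the later part of the curve is estimated from a favourable selection.

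OS is a stated secondary objective, and the trial has one arm, so there is no control curve that would share the distortion. The planned late update is where the problem would appear. The summary of changes lists the end-of-study rule under Sections 1.0, 2.1 and 5.8 and lists no matching change in Section 8.

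**Working it through.** **The plan's own figure.** The documents give no OS calculation. Their only design calculation is the ORR test. For at least 7 of 28 responses, the exact binomial gives power 0.908 at a true rate of 35% and type I error 0.0179 at 10%, in line with the stated 90% and 2.5%. It has no bearing on this point.

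**The rule as a formula.** Let a subject enter at calendar month e and approval fall at month T, so approval comes at a = T − e on the subject's own clock. Let x be the time on trial drug after approval (at most 6 months, Section 2.1) and f the safety follow-up (about 1 month, Section 7.1.5.4.1; 3 months if the 90-day SAE window counts). Leaving aside subjects off drug but still eligible for Second Course:

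- treatment stop: s = min(progression time, a + x)
- end of OS follow-up: max(a, s + f)

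A subject who progressed well before approval has s + f < a, so follow-up ends at a. A subject on drug throughout has s = a + x, so follow-up can reach a + 6 + 1 = a + 7 months (a + 9 with f = 3). A subject off drug in CR, or after 24 months, also passes a while Second Course remains possible.

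**Where bias can start.** With accrual period A, every subject has at least T − A months of potential follow-up at approval. Before that time nobody is censored by the rule. With T = 21 and A = 6, that is 21 − 6 = 15 months.

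**Size, assumed inputs.** None of these is in the documents: exponential PFS and post-progression survival, with medians of 4 and 6 months or 6 and 12 months; a pre-progression death rate of 0.5% per month; A = 6; T = 21. The runs use x = 6 and 400,000 simulated subjects per scenario. Bias is the Kaplan-Meier estimate under the rule minus true survival.

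| Month | Bias (points) | Expected at risk of 35 |
|---|---|---|
| 15 | 0 | – |
| 18 | +0.4 to +0.5 | – |
| 21 | +2.3 to +2.9 | 1.0 to 3.1 |
| 24 | +6.3 to +8.0 | 0.4 to 1.4 |

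For 28 cutaneous subjects, multiply the last column by 28/35 = 0.8: about 0.8 to 2.5 at 21 months and 0.3 to 1.1 at 24. Crossing the medians (4 with 12, 6 with 6) widens the bias to +0.2 to +0.8, +1.6 to +4.0 and +6.3 to +8.8 points at 18, 21 and 24 months. Censoring everyone at approval, with vital status known then, leaves at most 0.1 point of error at 15, 18 and 20.5 months.

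**Check against the documents' survival figure.** The inputs above imply 12-month OS of about 48-72%, whereas Section 4.1.1 reports more than about 80% alive at one year in the earlier melanoma study of this drug. A second set of 36 scenarios fixed 12-month OS at 80%, with median PFS 4, 6 or 12 months, approval at month 18 or 24, accrual over 4 or 8 months, and x and f of 6 and 1, 6 and 3, or 2 and 1 months. Bias was upward at every late time point in all 36:

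- half a month before the longest follow-up reached at approval: +0.2 to +5.7 points
- 3 months past it, with x = 6: +3.3 to +12.3 points, with 0.6% to 35% of subjects at risk (0.006 × 35 ≈ 0.2 to 0.35 × 35 ≈ 12)
- 1 month past it, with x = 2: +2.1 to +7.2 points

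One example is median PFS 6 months, approval at month 24, 4-month accrual, x = 6 and f = 1. At month 27 true survival is 0.479 and the rule gives 0.539, or +6.0 points. In trials of 28 subjects the rule averages 0.543, against 0.481 when everyone is followed to one date.

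**The case against.** A reader might infer that after approval only progression-free subjects remain at risk. The documents do not support that. Sections 5.8 and 7.1.3.4 let some subjects with confirmed progression continue on drug by exception, and let clinically stable subjects continue while progression is unconfirmed. Second Course subjects have progressed by definition. Those who progress near or after approval stay until safety follow-up ends. Conversely, subjects who stopped for toxicity without a CR have no Second Course route and end at approval without having progressed. The split is correlated with progression, not defined by it, and that correlation is enough to make censoring informative.

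A reader might also take the 6 to 8 points at 24 months as the error in the OS result. That figure belongs to a tail with about one subject or fewer at risk. Even with complete follow-up of 28 subjects, the standard error of 24-month survival, √(S(1 − S)/28), is about 7 to 9 points. Where the curve has support, the bias is nil to about half a point.

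OS has no test, comparator, landmark or alpha. Section 8.2.6 controls error for ORR alone, and Section 8.2.9 bases the filing decision on responses at the 24-week analysis. This objection stands, and it sets the importance of the point.

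Two defences fail. Section 5.10 defines when the overall trial ends, but the per-subject rule in Section 5.8 is mandatory and still removes subjects earlier. Section 8.2.9 fixes a main-analysis time and then plans further OS follow-up without a cut-off.

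**Conclusion.** The point holds as a minor one. Sections 2.1, 5.8 and 7.1.5.4.3, combined with the OS rows of Tables 8 and 9, produce censoring related to prognosis and an upward bias in the late OS curve. The mechanism comes from the plan's own rule, and the direction was the same in every scenario run.

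The size is conditional on the approval date, the delivery lag for marketed product and PFS, none of which the documents give. There is no bias before approval minus last entry, and none in an analysis cut at or before approval with vital status known for everyone. If marketed product arrives soon after approval, the extra follow-up is short and few subjects contribute to it. The documents do not support a conclusion that the OS analysis as a whole is unreliable, or that the ORR conclusion is affected.

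**What to change.** In Section 8.2.5.1 and the OS rows of Tables 8 and 9, state that every OS analysis, including the final update, uses one calendar cut-off for all subjects, no later than marketing approval. Ascertain vital status for every subject as of that date through one survival contact. Censor subjects alive then at the cut-off date, not at their last scheduled contact. Show numbers at risk with the curve.

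The vital-status step is needed. Subjects in survival follow-up are telephoned every 12 weeks while treated subjects are seen every 3 weeks, so censoring at the date last known alive would again depend on progression. In the month-21 approval scenarios, that version left about +0.6 points at 18 months and +1.3 at 20 if only deaths found at a contact count. If all deaths are captured, it left about −3 points at 18 months and −7 to −8 at 20.

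Following every subject to one later common date would also work, but it means extending survival contact past the per-subject end in Section 5.8.

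The cost is a short SAP amendment, one telephone contact per subject in survival follow-up, and a few months of post-approval follow-up in a few subjects that is not used for OS. Treatment and scheduled visits do not change.
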